2.6 RANDOMIZATION

Procedures Assuring Adherence to Randomized Assignment: Enrollment will occur in the prehospital phase of the trial and LTLR-WB or prehospital standard of care will be provided based upon randomization assignment. Prehospital providers will designate the patient as enrolled and notify receiving staff of the treatment arm. Research staff will be present upon arrival and will communicate directly with blood banking staff/anesthesia and the trauma team regarding the randomization arm of the patient. Once in-hospital, LTLR-WB randomized patients may receive LTLR-WB transfusion as indicated during this acute resuscitation phase of in-hospital care up to 6 units in-hospital and 8 units of LTLR-WB total.

Randomization and Blinding: A single stage cluster randomization scheme will be utilized. Designated air medical bases at the University of Pittsburgh will be block randomized and assigned to the LTLR-WB arm or Standard of Care (control) arm for 1 month time intervals. The cluster design will be at the level of the helicopter base. The block scheme will vary randomly between 2 and 4 month block sizes over the period of enrollment for the trial. Randomization assignments will be determined prior to the start of the bases enrollment following the above single stage cluster design using standard computerized randomization software. Communication with the blood bank transportation services and each respective air base will occur and an annual schedule of randomization assignment will be distributed to each study air base. This specific randomization scheme is required due to the limited supply of O+ LTLR-WB and also due to the logistics and delivery of the intervention in the prehospital setting. The

proposed pilot trial will be an open label trial as blood product transfusion requires appropriate documentation and essential look back procedures.

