lactate and shock index (SI, heart rate/systolic blood pressure-bpm/mmHg) 4) Acute Respiratory Distress Syndrome (ARDS): We will compare pulmonary dysfunction using the Berlin definition for ARDS.⁸⁶ 5) Nosocomial Infection (NI): We will compare the incidence of pneumonia and blood stream infections. 6) Mortality: We will compare mortality rates at 3, 6 and 24 hours following arrival, all cause in-hospital and 28-day mortality. 7) Blood component transfusion and resuscitation requirements at 24 hours: We will compare overall blood component transfusion requirements and crystalloid/colloid resuscitation requirements across the two arms. 8) Acute Hemolytic Transfusion Reaction (AHTR): We will compare the incidence of AHTRs across study arms as defined by the CDC/National Healthcare Safety Network (NHSN) Hemovigilance Surveillance definition. (www.cdc.gov/nhsn) Length of hospital stay and intensive care unit stay. Length of stay and ICU resources will be descriptively compared. Patients will be followed for 28 days from admission for the 28-day mortality outcome utilizing chart review, patient contact or utilization of the social security death index for those who cannot be contacted.

Predefined Subgroup Analyses: Predefined subset analyses for the pilot trial will be performed looking at our primary outcomes (safety/efficacy and feasibility) in 1) Females > 50 years of age versus study cohort with females < 50 years excluded ; 2) Patients who ultimately did or did not require in-hospital blood transfusion; 3) Patients with and without significant traumatic brain injury (Head abbreviated injury score- AIS >2); 4) Patients enrolled from the scene of injury versus those enrolled from a referral hospital; 5) Patients that require operative intervention in the first 24 hours; 6) Those patients with a preinjury history of anticoagulation / antiplatelet therapy; 7) Patients who ultimately did or did not require massive transfusion (≥ 10 units blood in first 24 hrs) 8)Patients who did or did not receive prehospital PRBCs.

Clinical Outcome Definitions:

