Estimates for Trial Secondary Clinical Outcomes: We will estimate the mean differences in the average Denver post-injury MOF score derived from the 3 highest daily scores between two treatment groups as the main clinical outcome for the pilot trial. We will also record and compare the overall proportion of patients who developed MOF based on Denver score > 3 and compare MOF free days. Similarly, the incidence of ARDS, NI, mortality (6hr, 24hr and 28 day) and hemolytic transfusion reactions will be recorded. We will perform survival analysis for all mortality outcomes. Blood component and resuscitation volumes over the initial 24 hours, length of ICU stay, days on a ventilator, and total hospital stay will be also be determined. Estimated proportions and means and 95% confidence intervals will be created for each outcome using the data from the entire pilot trial (i.e. combining the data from the two assigned treatment arms). Absolute and relative differences for continuous levels and event rates by assigned treatment will be estimated and 95% confidence intervals will be calculated to identify potential treatment differences for safety and for study planning purposes. Subgroup analyses will be exploratory and be based on baseline factors specified prior to the initiation of the trial.

The Following Outcomes Will Be Recorded:

- 1. The average Denver post-injury MOF score derived from the 3 highest daily scores. Differences between these averages will be estimated across the study two arms.
- Proportion of patients who developed MOF based on Denver score > 3 and compare MOF free days across the study two arms.
- 3. The incidence of ARDS, NI, mortality (6hr, 24hr and 28 day) and hemolytic transfusion reactions will be recorded and compared across the study two arms
- 4. Survival analysis in relation to all causes of death.
- 5. Blood component and resuscitation volumes over the initial 24 hours,
- 6. Length of ICU stay, days on a ventilator, and total hospital stay will be also be determined.

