3.2 INCLUSION CRITERIA

1. Injured patients at the risk of Hemorrhage being transported from scene or referral hospital to a participating PPOWER trial site

AND

2A. Systolic blood pressure \leq 90 mmHg AND tachycardia > 108 bpm at scene, or at outside hospital or during transport.

OR

2B. Systolic blood pressure ≤70 mmHg without tachycardia requirement, at scene or outside hospital or during transport.

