3.3 EXCLUSION CRITERIA

- 1. Documented age: Age ≥90 or <18 years of age
- 2. Inability to obtain intravenous or interosseous access
- 3. Isolated fall from standing injury mechanism
- 4. Known prisoner or known pregnancy
- 5. Traumatic arrest with > 5 minutes of CPR without return of vital signs
- 6. Brain matter exposed or penetrating brain injury (GSW)
- 7. Isolated drowning or hanging victims
- 8. Isolated burns without evidence of traumatic injury
- 9. Referral Hospital In-patient admission
- 10. Objection to study voiced by subject or family member at scene
- 11. Wearing PPOWER opt-out bracelet

Inclusion and exclusion criteria will be assessed based on available information at the time of enrollment. Although all reasonable efforts will be made by the air medical crew to either directly witness or obtain documentation of eligibility criteria, due to the nature of the emergency pre-hospital setting, there may be occasions where the air medical crew must rely on verbal report of inclusion criteria, including qualifying vitals, from the referring hospital or ground crew. In these instances, if, after subsequent review of outside hospital and/or ground crew documentation, it is determined that the subject did not meet inclusion criteria and/or met exclusion criteria, the subject will remain enrolled in the study based on the intention-to-treat principle.

In the event that a verbal report must be used in lieu of physical documentation or directly witnessing the qualifying vitals, documentation of the verbal report will serve as the source documentation for determining eligibility. Verbal reports will be documented in the air medical record and will detail the information reported and by whom.

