6.4.6 Adverse Events Reporting Timeline

Organization	Fatal/Life Threatening SUSAR	Non-fatal, non-life threatening SUSAR	SAE (expected and related)	UP (not involving risk)	UPIRTSO
IRB	24 hours	10 working days	No requirement	No reporting**	10 working days
FDA	7 calendar days	15 calendar days	No requirement	No requirement	14 days*
NHLBI	7 calendar days	7 calendar days	No requirement	No requirement	14 days*
Medical Monitor	24 hours	7 calendar days	No reporting	No reporting	14 days*
DSMB	24 hours	7 calendar days	At next meeting (every 6 months)	At next meeting (every 6 months)	14 days*

A table summarizing reporting timelines is provided below:

*Reporting occurs only after an IRB determination of UPIRTSO has been received

**No direct reporting is required; events are documented on a log that can be reviewed upon request

Prehospital Transfusion Adverse Events/Look Back Standard Operating Procedure (SOP):

a. Transfusion rate will be compatible with the patient's condition. The patient will be monitored closely during the entire transfusion. The documented start and stop times are directly related to the actual transfusion of the component. Study coordinators will assume responsibility of additional vital signs and completion of the whole blood

b. The patient medical record shall include the following:

- 1. Name of the components transfused
- 2. Donation identification number
- **3.** Date and time of transfusion (Start and Stop time)
- 4. Pre and post transfusion vital signs
- **5.** The volume or **#** of units transfused
- 6. The transfusionist's name (paramedic)
- 7. Documentation of related adverse events

c. Procedure for transfusion reactions:

This is modified from UPMC policy for Blood Transfusions to be applicable for this study.

1. Careful observation throughout the transfusion allows for early detection of adverse reactions and optimal treatment, if necessary. All reactions should be handled initially as possible hemolytic reactions and the transfusion must be stopped. Any adverse events associated with the transfusion of blood or blood components should be documented in the patient's Medical Record and reported to the blood bank/ transfusion service. Prehospital providers initiating transfusion of blood products will monitor vitals

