6.5.1 Protection Against Risks

General Risks of Study Protocol and Procedures

Data collected will include a review of the air medical patient care report(s), Emergency Department and electronic/ paper hospital records. Prehospital Data: Demographics, air medical response times (call receipt to arrival, arrival at patient side,) injury characteristics, vital signs, prehospital resuscitation volumes, prehospital interventions (needle decompression, chest tubes)

referring hospital vitals, and interventions will be recorded. In-Hospital Data: Demographics, shock severity (base deficit, lactate), injury characteristics, ED vitals, ED interventions (chest tubes, intubation), injury severity, operative interventions and timing of interventions, injury severity score, ICU days, ventilator days, length of stay, multiple organ dysfunction scores (daily), nosocomial infectious outcomes, blood gas results, chest x-ray reads, transfusion of blood and blood components, resuscitation requirements, all primary and secondary outcomes will be recorded.

Data Entry and Storage: MACRO and associated internet technology affiliates at the University of Pittsburgh will create web-based data entry platform to collect necessary information for the proposed pilot study.

All research interventions/activities will be conducted in private patient care areas. The collection of sensitive information about subjects is limited to the amount necessary to achieve the aims of the research, so that no unneeded sensitive information is being collected.

A Case Report Form will be completed for each subject enrolled into the clinical study. The Investigator will attest that all clinical and laboratory data entered on the CRF are complete, accurate and authentic using a signoff page within the data entry platform. A key linking the subject to the code number will be kept locked in a secure location and will be available only to the investigators. The data and samples will be retained indefinitely and used for future testing. Data from this study, without the subject's identity, may be reported in scientific meetings, articles or other appropriate communications.

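### Arrival shock index would be compared without using the pre-treatment vital signs the trial already records, so the estimate is less precise than it could be and starting shock by arm is not shown

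*Combined protocol and SAP*

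**What the plan says.** Section 2.8 (Secondary Clinical Outcomes, item 3) lists presenting base deficit, "lactate and shock index (SI, heart rate/systolic blood pressure-bpm/mmHg") as measures to be compared between arms. It names no method. The general rule for secondary outcomes in section 2.9 is: "Absolute and relative differences for continuous levels and event rates by assigned treatment will be estimated and 95% confidence intervals will be calculated". No covariate is named anywhere, and baseline characteristics are only described. Arrival shock severity is also absent from the list of recorded outcomes in 2.9 and from Table 4 of Appendix 8. Table 1 has no prehospital blood pressure, heart rate or shock index.

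Pre-treatment values do exist:

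- Section 3.2, route 2A, requires systolic pressure of 90 mmHg or below "AND tachycardia > 108 bpm at scene, or at outside hospital or during transport".
- Route 2B requires 70 mmHg or below, "without tachycardia requirement, at scene or outside hospital or during transport".
- Section 6.5.1 lists "injury characteristics, vital signs, prehospital resuscitation volumes" among the prehospital data, together with referring-hospital vitals.
- The transfusion procedure in 6.4.6 asks for "Pre and post transfusion vital signs" in the medical record, which covers transfused patients only.

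Section 3.3 allows that crews sometimes "must rely on verbal report of inclusion criteria, including qualifying vitals". Under section 2.6, bases are "assigned to the LTLR-WB arm or Standard of Care (control) arm for 1 month time intervals", open label, on an annual schedule sent to each base.

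**The concern.** Arrival shock index is an early haemodynamic readout of the prehospital product, and the secondary estimates are meant to inform the larger trial. Patients enter at different depths of shock. Route 2A implies a qualifying shock index above 108/90 = 1.2, while route 2B has no heart-rate floor. They also come from the scene or from a referral hospital. If qualifying shock index predicts arrival shock index, a plain arm difference leaves that explained variation in the error term.

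There is a second, more visible consequence. Without qualifying vitals by arm in Table 1, a reader of the results cannot judge whether the two arms began equally shocked. That matters more than usual because assignments are known to crews in advance.

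**Working it through.** **The plan's own figure.** The documents give no power or precision figure for shock index. The only one is for mortality (section 2.9): 33% versus 11%, 56 per arm. Its drift is 0.22 / √(2 × 0.22 × 0.78 / 56) = 2.81024, as printed. With the printed boundaries of 2.96259 and 1.96857, total power comes to 0.8010 against the stated 0.800921. This confirms 56 per arm as the working size and says nothing about shock index.

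**Inputs.** n = 56 per arm (section 2.9). The correlation ρ between qualifying and arrival shock index is not in the documents, so a range is assumed. Results are in units of the SD of arrival shock index and treat patients as independent.

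**Unadjusted.**
- 95% half-width: 1.96 × √(2/56) = 0.370 SD.
- Difference detectable with 80% power: (1.960 + 0.842) × √(2/56) = 0.529 SD.

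**Adjusted for qualifying shock index.** Residual variance is multiplied by 1 − ρ², both quantities above by √(1 − ρ²), and the equivalent unadjusted size is 56 / (1 − ρ²).

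| ρ (assumed) | Variance reduction | Half-width (SD) | Detectable difference (SD) | Equivalent n per arm |
|---|---|---|---|---|
| 0 | 0% | 0.370 | 0.529 | 56 |
| 0.2 | 4% | 0.363 | 0.519 | 58.3 |
| 0.3 | 9% | 0.353 | 0.505 | 61.5 |
| 0.5 | 25% | 0.321 | 0.459 | 74.7 |

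**Where in the range.** The entry cut-offs narrow the spread of qualifying shock index, which lowers ρ. An illustrative simulation with assumed vital-sign distributions gave ρ of 0.36 to 0.65 in all patients but 0.20 to 0.42 in those meeting 2A or 2B. That is a variance reduction of 0.20² = 4% to 0.42² = 18%. The lower part of the table is therefore the more plausible part.

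**Why not a change score.** Its variance relative to the raw arrival value is 2(1 − ρ) when the SDs are equal: 1.6 at ρ = 0.2 and 1.0 at ρ = 0.5. Below 0.5 it is noisier than doing nothing. Covariate adjustment is not.

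**Carry-over of a baseline gap.** The standard error of a chance gap in qualifying shock index is √(2/56) = 0.19 SD. A gap of 0.2 SD moves the raw arrival difference by ρ × 0.2, or 0.1 SD at ρ = 0.5 with equal SDs. The unadjusted half-width is 0.370 SD.

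**The case against.** The strongest reply is that nothing here is wrong. An unadjusted comparison of randomized arms is valid, this is one of several secondary outcomes in a pilot, and adjustment is a refinement. That stands, and it limits the point to precision and reporting.

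Several stronger readings are tempting, but the documents do not support them:

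- *Every patient has a pre-treatment shock index.* Only systolic pressure is required of all. Route 2B needs no heart rate, vitals may be verbal, and section 5.1 allows enrolment by research staff after arrival in the emergency department. Some heart rates may be missing.
- *Base-month allocation makes the raw comparison misleading.* The confidence interval already allows for chance imbalance, and a 0.1 SD shift is small beside 0.370 SD. The number of bases is not stated. With 3 to 8 assumed over 30 months, 112 patients give 112/90 = 1.24 to 112/240 = 0.47 per base-month, so imbalance from clustering alone should be small.
- *Adjustment removes imbalance.* It reduces imbalance in the measured covariates. It cannot remove unmeasured selection by crews who know the month's assignment.
- *Verbal-report error merely adds noise.* Those who take the reports can know the arm, so error unrelated to arm cannot be assumed.
- *Baseline information is ignored altogether.* Table 1 reports transfer status, GCS and ISS by arm, and scene versus referral is a predefined subgroup, although for the primary outcomes only.

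**Conclusion.** The point holds as a low-cost improvement. The plan names no analysis for arrival shock severity. Its general rule implies an unadjusted difference, although most or all patients will have a usable qualifying shock index. The gain in precision is modest: 4 to 25% less residual variance for an assumed correlation of 0.2 to 0.5, more likely toward the lower end. This rests on the assumed correlation, on independent patients, and on baseline measurement good enough to be predictive. Missing or inaccurate heart rates would reduce it. No gain can be claimed for lactate or base deficit, because the documents describe no pre-treatment value for either.

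The reporting gap does not depend on any assumption: the tables show neither qualifying shock nor arrival shock by arm. The mortality analysis, sample size and stopping boundaries are untouched.

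**What to change.** In section 2.9, before any comparison by arm is seen:

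- Specify a linear model for arrival shock index with assigned arm, qualifying shock index and scene versus referral origin. Use standard errors that respect the base and base-month allocation.
- If entry severity is also included, define it without overlap, for example qualifying systolic pressure at or below 70 versus above 70 mmHg. A 2A/2B indicator is ambiguous for patients who meet both routes.
- State a rule for missing qualifying heart rate that keeps all patients in the analysis, such as baseline imputation with a missing indicator.
- Use the same covariates for arrival lactate and base deficit, without claiming a precision gain.
- Report the unadjusted difference beside each adjusted one.

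In Appendix 8, add qualifying systolic pressure, heart rate and shock index by arm to Table 1, and arrival shock index, lactate and base deficit to Table 4.

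The cost is a short paragraph and a few table rows, with no data collection beyond the prehospital vitals already planned. The downside is reliance on some verbally reported vitals whose error may differ by arm, which is why the unadjusted result should stay in view.
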